Health care reform under the Patient Protection and Affordable Care Act (ACA) offers considerable opportunities for colorectal cancer survivors to obtain coverage and improve access to needed care. However, in the general population, many people have low understanding of available insurance benefits and resources and have limited health insurance literacy (i.e. perceived knowledge, ability, and confidence to make informed decisions about choosing and using health insurance).¹⁵ Misperceptions about which services require out-of-pocket costs may lead some enrollees to avoid services that are in fact exempt from cost sharing. For colorectal cancer survivors are particularly vulnerable to financial burden related to low health insurance literacy.¹⁴ For colorectal cancer survivors, having a proficient understanding of health insurance is necessary for obtaining adequate health insurance to meet follow-up and surveillance needs without experiencing a significant degree of financial burden

2. Specific Aims and Objectives

Aim 1: To conduct an open pilot of a videoconferencing-based randomized trial of the health insurance navigation tools program with approximately 5 colorectal cancer survivors.

A1a: To assess the preliminary feasibility and acceptability of the HINT intervention via the measures and methods described below

A1b: To utilize open pilot feasibility and acceptability data to inform Aim 2 (RCT) methodology

Aim 2: To conduct a videoconferencing-based randomized trial of the health insurance navigation tools program (HINT) (n= approximately 60).

A2a: To assess the feasibility (number of eligible enrolled and sessions completed) and acceptability (satisfaction, perceived support) of participants undergoing a health insurance navigation tools program (HINT).

A2b: At 3-month post-program follow-up, to assess the efficacy of the HINT to assist participants with accessing and utilizing coverage and managing costs. Primary outcomes are 1) health insurance literacy and 2) financial distress related to medical costs. A2b Hypothesis: The HINT, compared to enhanced usual care, will improve participants’ health insurance literacy and decrease financial distress.

3. General Description of Study Design

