Open Pilot Design: We will recruit approximately 5 colorectal cancer survivors from Massachusetts General Hospital via the Research Patient Data Registry (RDPDR) to take part in a health insurance navigation intervention. Recruitment, consent, and intervention approach for the pilot will mirror the trial design, as described below. The purpose of the open pilot is to inform any changes in the trial and program approach prior to implementing the randomized pilot trial.

Randomized Trial Design: We will recruit and randomize approximately 60 colorectal cancer survivors from Massachusetts General Hospital via the Research Patient Data Registry (RDPR) to a health insurance navigation intervention or to enhanced usual care (Please see Sections III and IV for information on subject selection and consenting procedures). We have selected this sample size of approximately 40 per arm to enable evaluation of feasibility and acceptability goals as well as explore meaningful differences in the outcomes.⁷⁸ Surveys will be conducted at baseline and 3-month post program completion follow-up via REDCap or mail. All participants will be asked to complete a follow-up survey approximately 3-months after the HINT intervention period (in other words approximately 5-months post pilot trial enrollment). Participants will be remunerated \$20 for each survey.

Study Arms

Enhanced Usual Care

Enhanced usual care will consist of a mailed or emailed copy of a health insurance booklet.

Navigation Intervention

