Records include patient’s medical record numbers, demographic characteristics, diagnoses (code and encounter date), inpatient and outpatient encounters, and other medical care. Approximately 65 (5 for the open pilot, 60 for the RCT) participants meeting these criteria will be identified and recruited. We will exclude participants who: (1) do not speak English, (2) do not have health insurance, (3) are under the age of 18, (4) are over the age of 65, (5) are unable to give informed consent due to psychiatric, cognitive, or medical (ie. Patient in hospice at end of life) impairment as determined in consultation with study PI, patient navigator, or oncology social worker, and (6) do not have access to a smartphone, computer or tablet with internet access. The rationale for the third exclusion criterion is that an intervention with a large number of Medicaid-eligible survivors would be outside the scope of the current intervention. The rationale for the fifth exclusion criterion is that the health insurance navigation intervention is delivered via an MGB-approved video-conferencing system (ie. Zoom).

A member of the research team will review the electronic medical record (i.e., EPIC) to ensure that identified patients are eligible for the study before proceeding with outreach. A team member will confirm that the patient is alive and has not been hospitalized within the past year due to psychiatric reasons.

Sources of Subjects and Recruitment Methods

The Research Patient Data Registry is a centralized clinical data registry that stores and gathers patient information from across the Mass General Brigham system. It provides clinical researchers the ability to perform population queries and identify target subpopulations for research studies. Research Options Direct to You [RODY] patients and self-referred within the RDPR will be contacted about the study.

5. Subject Enrollment

Methods of Enrollment

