Potential participants will be identified via the Mass General Brigham RDPR. Patients among the Research Options Direct to You (RODY) designation within the RDPR will receive an opt-out letter from the study team. This letter (See Recruitment Letters) will describe the study procedures and ask patients to contact the study team within 3 days if they would not like to be contacted further about the study. Those who do not opt-out will be contacted via encrypted email or by phone by the PI or by a trained and CITI-certified research staff member, and they will be read or sent a brief description of the study (See Study Description Documents).

Patients may also express interest in the study by contacting the research team directly.

Patients who are interested will be screened for eligibility, and those who are eligible will undergo informed consent. Specifically, eligible and interested patients will be asked to review the study fact sheet by phone with a study team member. Once that is completed, the study fact sheet will be sent to participants in an encrypted / unencrypted email, depending on their preference (see HINT C Short Consent). This method of obtaining consent has been used in other IRB-approved trials, like 2018P000539). Following consent, enrollees will be assigned a unique study identification number and will complete a baseline assessment. Patients who consent and complete the baseline assessment will then be randomized into the intervention or control arm.

The study interventionist will contact consented participants randomized to the intervention via unencrypted or encrypted email to schedule the HINT sessions, again depending on patient preference. To facilitate communication with the oncology team, the interventionist will complete a summary documentation note within EPIC informing clinicians of the patients' participation in the program. We will send reminder notices via calls, emails, mail, and Patient Gateway for participants who have not completed the baseline survey or for those in the intervention arm who have not scheduled their sessions, as needed (see "HINT C Difficult to Reach Letter").

Privacy protection: To address security issues related to email communication, participants will be informed about security in the opt-out letter itself via inclusion of the following text:

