"Please note that emails sent to the study staff from your personal email address may not be secure and could result in the unauthorized use or disclosure of your information. If you want to email the study team despite these risks, Partners HealthCare will not be held responsible. If you do not want to email the study team, you may instead call [XXX RA's phone number]".

For any emails sent by the study team, they will be encrypted using Send Secure unless patients verbally agree to receive unencrypted email, which we will document. Patients will receive the following information:

"The Partners HealthCare standard is to send email securely. This requires you to initially set up and activate an account with a password. You can then use the password to access secure emails sent to you from Partners HealthCare. If you prefer, we can send you "unencrypted" email that is not secure and could result in the unauthorized use or disclosure of your information. If you want to receive communications by unencrypted email despite these risks, Partners HealthCare will not be held responsible. Your preference to receive unencrypted email will apply to research studies for emails sent to you from research staff in this study. If you wish to communicate with other research staff at Partners regarding additional studies, your preference will have to be documented with each research group."

Informed Consent

Eligible and interested patients will be asked to review the study fact sheet by phone with a study team member. Once that is completed, the study fact sheet will be sent to participants in an encrypted / unencrypted email, depending on their preference (see HINT C Short Consent). This method of obtaining consent has been used in other IRB-approved trials, like 2018P000539).

Intervention Assignment and Randomization

Using the RDPR, MGH staff will outreach to patients meeting the eligibility criteria and query terms. For the randomized pilot trial, the 60 participants will be randomized to either enhanced usual care (n=40), or the health insurance navigation intervention (n=40). Randomization will employ a random plan generator, with consented patients being randomly assigned to either the enhanced usual care or the health insurance navigation intervention, stratified by age (18-39 and 40-65).

6. Study Procedures

Navigation Intervention

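### The randomized trial is sized at 60 in total but 40 in each of two arms, which makes 80; the only size rationale is tied to 40 per arm

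*Combined protocol and SAP*

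**What the plan says.** The trial total is 60 wherever a total is given:

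- Section 2, Aim 2: "To conduct a videoconferencing-based randomized trial of the health insurance navigation tools program (HINT) (n= approximately 60".
- Section 3, Randomized Trial Design: "We will recruit and randomize approximately 60 colorectal cancer survivors from Massachusetts General Hospital".
- Section 4, inclusion and exclusion criteria: "Approximately 65 (5 for the open pilot, 60 for the RCT) participants meeting these criteria will be identified and recruited".
- Section 5, Intervention Assignment and Randomization: "the 60 participants will be randomized to either enhanced usual care (n=40), or the health insurance navigation intervention (n=40".

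The last of these also gives the arm sizes as 40 and 40. Section 3 gives the same arm size in its only statement of why this sample size was chosen: "We have selected this sample size of approximately 40 per arm to enable evaluation of feasibility and acceptability goals". That sentence adds the aim of exploring meaningful differences in outcomes.

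There are two arms, and participants are "randomly assigned to either the enhanced usual care or the health insurance navigation intervention, stratified by age (18-39 and 40-65". No allocation ratio is stated. Section 9 (Statistical Analysis) contains no sample-size statement.

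**The concern.** The total and the arm sizes cannot both be right, and they stand side by side in two separate sections. Staff following the protocol cannot tell whether to stop randomizing at 60 or at 80. No randomization list can give both 60 in total and 40 in each of two arms. Stopping at 60 leaves the arms short of the stated 40 on average; going on to 80 exceeds every stated total.

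The rationale is affected too. If 60 is right, the only argument for the sample size describes arms one third larger than the trial will have. If 40 per arm is right, the trial totals in Sections 2, 3, 4 and 5 are each 20 too low.

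**Working it through.** **Inputs.** Trial total 60 (Sections 2, 3, 4 and 5); open pilot 5 and overall total 65 (Section 4); arm size 40 (Sections 3 and 5); two arms (Sections 3 and 5).

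**Step 1: reproduce the plan's figures.**
- Overall total: 5 + 60 = 65, as Section 4 states.
- Trial total from the arms: 40 + 40 = 80, against a stated 60. The difference is 20, and 20/60 = 33%.

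**Step 2: look for a reading that reconciles 60 with 40 + 40.**
- *Rounding.* Sections 2, 3 and 4 call the totals approximate, but that cannot cover a 33% gap. Section 5 gives 60, 40 and 40 with no such qualifier.
- *Loss to follow-up (80 randomized, 60 completing).* This needs a loss of 1 − 60/80 = 25%. No dropout rate is stated, and Sections 3 and 5 use 60 for the number randomized.
- *Loss before randomization.* Section 5 says "Patients who consent and complete the baseline assessment will then be randomized into the intervention or control arm", so losses at consent or baseline come before allocation. The 40s are attached to the randomized arms.
- *Unequal allocation or a third arm.* Both arms are given as 40, and only two are described.
- *Counting the open pilot.* 5 + 80 = 85, not 65.

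None of these works.

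**Step 3: the two consistent versions, assuming equal arms.**

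| | Total 60 kept | 40 per arm kept |
|---|---|---|
| Randomized | 60 | 2 × 40 = 80 |
| Per arm | 60/2 = 30 | 40 |
| With open pilot | 65 | 85 |

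The ratio of arm sizes is 40/30 = 1.33.

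**Step 4: what the difference means for precision (illustration only).** The protocol gives no alpha, power, SD or attrition, so the inputs here are assumed.
- Confidence intervals widen by √(40/30) = 1.155, about 15%.
- For a proportion within one arm, such as an acceptability rate, the Wilson 95% half-width is 13.9 points at n = 30 and 12.1 at n = 40 for an observed 80%. For an observed 50% it is 16.8 and 14.8.
- For a two-sample t-test at two-sided 5% and 80% power with no loss, the normal approximation (1.960 + 0.842) × √(2/n) gives a detectable difference of 0.72 SD at 30 per arm and 0.63 SD at 40. The exact t calculation gives 0.74 and 0.63 SD. With an assumed 10% to 20% loss, the exact values become 0.78 to 0.83 SD and 0.67 to 0.71 SD.

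**The case against.** The best defence is that the total is not really in doubt. Sixty appears in four sections, Section 4 breaks 65 down exactly, and 80 is written nowhere. On that view the 40s are stray figures and the recruitment target is clear. The statistical harm is also limited. The outcome measures in Section 6 make feasibility and acceptability primary, Section 9 is largely descriptive, and no stated power calculation fails.

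Much of this stands. The repetition makes 60 the better-supported figure, and the loss of precision is modest. But nothing in the document shows that the 40s are left over from elsewhere. They appear in two sections, and one of those carries the only sample-size rationale. Efficacy is not incidental either: Aim 2 in Section 2 names two efficacy outcomes as primary and states a directional hypothesis. Even a descriptive pilot needs one enrolment number.

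A further fair point is that keeping 60 takes more than replacing a numeral. The rationale is qualitative, and its citation reads as 78 in the available text while the reference list ends at 32. The document therefore cannot show whether 30 per arm meets the stated goals, and the sponsor has to confirm that it does.

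**Conclusion.** The contradiction is certain and rests on no assumption: 40 + 40 = 80, not 60, a gap of 20 participants. It must be corrected because the sample size is a core design figure and the randomization sentence cannot be executed as it stands.

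Which figure was intended is not proven. Repetition and the 65 favour 60; the rationale favours 40 per arm. The figure of 30 per arm assumes equal allocation, which the equal arm sizes imply but the text does not state. The precision and detectable-difference figures rest on assumed inputs. They show the scale of the consequence, and the conclusion does not depend on them.

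**What to change.** The sponsor should confirm the intended size, then state one total, the allocation ratio and matching arm sizes identically in Sections 2, 3, 4 and 5.

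- **If 60 is confirmed (better supported):** keep 60, and 65 with the open pilot. Replace the 40 per arm in Section 3 and both arm sizes in Section 5 with about 30, and rewrite the Section 3 rationale for 30 per arm, including confirmation that this size still serves the feasibility, acceptability and exploratory goals. The cost is text changes and a short re-justification; no extra participants are needed.
- **If 40 per arm is confirmed:** change every trial total to 80 and the overall total to 85. The cost is 20 more participants than the stated total, with the recruitment effort that goes with them. At two surveys and $20 each, payments rise by 20 × 2 × $20 = $800. Ten more intervention participants at up to 5 sessions of about 30 minutes add up to 50 sessions, or about 25 hours of navigator contact.

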The intervention will be delivered via synchronous videoconferencing (real-time delivery and communication between the navigator and the participant) by a trained patient navigator (See Intervention Fidelity in Section VI) and will consist of 5, approximately 30-minute sessions delivered every week or two, over the span of approximately one month (See Table 1: Proposed HINP Intervention). The sessions will occur one-on-one between the navigator and the participant and will be interactive (i.e. participants will be able to ask questions and respond to content throughout the sessions). The proposed program content was informed by the following: 1) aforementioned research on the associations between financial burden and health insurance literacy among colorectal cancer survivors, 2) CCSS health insurance survey, 3) ACA provisions that are relevant to survivors (e.g., prevention services exempted from cost sharing, sources of available coverage and eligibility, benefits policies that have cost-related implications like OOP costs, and essential health benefits such as prescription medications), and 4) an ongoing randomized pilot trial of the program with survivors of childhood cancer. The navigation intervention group will also receive a mailed copy of the health insurance booklet given to the enhanced usual care arm.

Table 1: Proposed HINT Intervention
Session One: Learning About Survivorship Healthcare Needs
Sessions Two: Learning About Your Plan in Relation to Policy
Session Three: Navigating One's Own Plan
Session Four: Managing Care Costs

4. Subject Selection

Participants: Inclusion and Exclusion Criteria

Study participants will be identified via the online query tool of the RDPR for both the open pilot and randomized trial. Patients who are 1) **approximately** 6 months to 5 years posttreatment for stages I-III colon or rectal cancer or 2) **approximately** more than **3 months** post-diagnosis for stage IV colon or rectal cancer at the time of screening will be eligible. We will constrain records to patients who have (a) had a medical visit at a MGH Cancer Center (ie. MGH Boston, Danvers, Waltham or Mass General Cancer Center at Newton-Wellesley) in the past two years, (b) an ICD diagnostic code of colorectal cancer (i.e.,

malignant neoplasm of the colon, rectum, or rectosigmoid junction), and (c) a pathology report with the terms “stage I”, “stage one”, “stage II”, “stage two”, “stage III” or “stage three”.

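### Stage I-III post-treatment and stage IV patients enter by different routes, but entry route is neither a stratification factor nor a named covariate, so any imbalance would be handled post hoc

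*Combined protocol and SAP*

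**What the plan says.** **Eligibility (Section 4).** There are two routes in. The first is about "6 months to 5 years posttreatment for stages I-III colon or rectal cancer". The second sets a minimum of roughly 3 months "post-diagnosis for stage IV colon or rectal cancer at the time of screening will be eligible". The second route has no off-treatment condition and no upper time limit. The registry query in the same section nevertheless requires "a pathology report with the terms “stage I”, “stage one”, “stage II”, “stage two”, “stage III” or “stage three", so it contains no stage IV term.

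**Allocation (Section 5, Intervention Assignment and Randomization).** "Randomization will employ a random plan generator", and allocation is "stratified by age (18-39 and 40-65". Block size is not given. No other balancing factor appears anywhere.

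**Analysis (Section 9).** The arms are to be described at baseline and any imbalance adjusted for, with no variable, threshold or model named. Efficacy changes are compared between arms by independent t-test and chi-square. Bivariate analyses will relate sociodemographic and cancer-related factors to the outcomes; stage and treatment status are not among the examples.

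**Measures (Section 6).** Cancer diagnosis and treatment type are listed. Stage, and whether treatment is ongoing, are not.

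**Size.** Section 2 plans "To conduct a videoconferencing-based randomized trial of the health insurance navigation tools program (HINT) (n= approximately 60". Sections 3 and 5 speak of 40 per arm.

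**The concern.** The eligibility rule itself separates patients who have finished treatment from patients who may still be receiving it. The two groups are likely to differ in ongoing medical costs. Financial distress related to medical costs is one of the two outcomes that Aim A2b is built on, although Section 6 ranks it as secondary. Entry route is therefore a plausible prognostic factor for an outcome the trial wants to compare, and it is known before randomization.

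In a trial this small, allocation unrelated to entry route can leave the arms visibly different on it. The plan's only response is to look at the baseline table and then decide what to adjust for. That leaves the covariate set to be chosen after the data are seen. It also gives no assurance that entry route would be examined, and the two tests it names take no covariate. What is at stake is how the efficacy comparison can be read if the arms come out unequal, and some precision if they do not.

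**Working it through.** **Plan's own figure.** The plan gives no figure for balance on stage. The only relevant stated number is the sample size, and it does not add up: 40 + 40 = 80, not 60. Both 30 per arm (60 in total) and 40 per arm (80 in total) are therefore carried through.

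**Inputs.**
- From the documents: total of 60 or 80; two arms of equal planned size; age the only stratification factor.
- Assumed, because the documents give no value: stage IV share of 10%, 20% or 30%; stage IV shift in the change score of 0.5 to 0.8 SD.

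**Step 1: chance of imbalance.** With allocation unrelated to stage, the number X of the K stage IV patients who fall in one arm is hypergeometric (N patients, K stage IV, n = N/2 per arm). The arm difference in stage IV share is |2X - K| / n. K is even in every case below, so the difference in counts is always even.

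| Per arm | Share | K | SD of difference | P(10 points or more) | P(20 points or more) |
|---|---|---|---|---|---|
| 30 | 10% | 6 | 7.8 points | 0.195 | 0.024 |
| 30 | 20% | 12 | 10.4 points | 0.333 | 0.104 |
| 30 | 30% | 18 | 11.9 points | 0.399 | 0.158 |
| 40 | 10% | 8 | 6.8 points | 0.263 | 0.005 |
| 40 | 20% | 16 | 9.0 points | 0.402 | 0.048 |
| 40 | 30% | 24 | 10.3 points | 0.465 | 0.087 |

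At 30 per arm, 10 points is 3 patients, so the smallest even difference that counts is 4 (for K = 12, a split of 8:4). Twenty points is 6 patients (9:3). At 40 per arm, 4 patients is exactly 10 points. That discreteness is why the 10-point probabilities are higher in the larger trial; the SD column shows that the imbalance itself is smaller.

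**Step 2: effect on the contrast.** Shift = imbalance × stage IV effect.
- 0.20 × 0.5 = 0.10 SD
- 0.20 × 0.8 = 0.16 SD

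The standard error of a difference in means is √(2/n): √(2/30) = 0.258 SD and √(2/40) = 0.224 SD. The shift is therefore 0.10/0.258 = 0.39 to 0.16/0.258 = 0.62 SE at 30 per arm, and 0.10/0.224 = 0.45 to 0.16/0.224 = 0.72 SE at 40 per arm.

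**Step 3: precision gained by adjusting.** With within-route SD 1, share p and stage IV effect g, leaving route out inflates the outcome variance to 1 + p(1 - p)g². The relative cut in SE from adjusting is 1 - 1/√(1 + p(1 - p)g²).
- Smallest case: p = 0.1, g = 0.5: 0.09 × 0.25 = 0.0225, a cut of 1.1%.
- Largest case: p = 0.3, g = 0.8: 0.21 × 0.64 = 0.1344, a cut of 6.1%.

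These figures are before the cost of estimating one more coefficient. With one covariate that cost is roughly √(1 + 1/(N - 4)) - 1, which at N = 60 is √(1 + 1/56) - 1 = 0.9% of the SE. In the smallest case the gain is therefore close to nil.

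**Step 4: what re-stratifying would do.** A simulation (5,000 runs per setting; blocks of 4, 20% aged 18-39, and stage independent of age, all assumed) compared age-only with age-by-route strata at 60 patients. For shares of 10%, 20% and 30%, the chance of a 10-point or larger imbalance was 24%, 39% and 45% with age only, and 0.5%, 0.5% and 0.3% with both factors. The age-only figures differ from the exact ones because the number of stage IV patients and the arm sizes vary from run to run. The largest difference in arm size rose from 4 to between 6 and 8.

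**The case against.** Leaving a prognostic factor out of stratification is not a validity flaw. The t-test's standard error already contains the variation from chance imbalance, and even the 20-point case moves the estimate by well under one SE. Section 9 compares changes, so a stable difference in the level of financial distress largely cancels; stage would have to alter the change itself. The query lists only stage I-III terms, so few stage IV patients may be found, although self-referral is allowed. Section 9 does promise adjustment and does plan analyses by cancer-related factors. All of this stands, and it keeps the point modest. It does not supply a named covariate or a model: the bivariate analyses relate factors to outcomes and do not adjust the arm comparison.

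A reader might infer more than the documents support:
- **That the efficacy contrast is biased.** It is not, on average over randomizations. The shift in Step 2 belongs to one unlucky allocation.
- **That sessions completed would be distorted between arms.** Sessions exist only in the navigation arm; the control arm receives a booklet. There is no such contrast.
- **That stratifying would protect against lost follow-up.** Neither stratification nor adjustment restores missing surveys. Differential dropout by route is possible, but nothing in the documents shows it.
- **That the content does not fit stage IV patients.** The title "Session One: Learning About Survivorship Healthcare Needs" does not establish that.
- **That the allocation list must be rebuilt.** Four strata in about 60 patients leave sparse cells and larger arm-size differences, and small blocks make allocation easier to predict. This is a matter of judgment.

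**Conclusion.** The point holds as a cheap improvement to the analysis plan. The eligibility rule creates two groups likely to differ in ongoing medical costs; allocation ignores that split, and the analysis covers it only through unspecified adjustment after the baseline data are seen.

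The size depends on a stage IV share that the documents do not give. At 10%, a 20-point imbalance is unlikely (0.5% to 2%); at 20-30% it is a 5% to 16% event across the two possible sample sizes. The effect on the contrast and the gain from adjusting rest on an assumed 0.5-0.8 SD difference in change, and both are modest. The main gain is that the covariate is fixed beforehand. The effect falls on the efficacy comparison, which Section 6 calls secondary and Section 2 calls primary.

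**What to change.** **In Section 9**, replace post hoc adjustment for this factor with a prespecified model. For continuous efficacy outcomes, use an ANCOVA or linear regression on arm, entry route (stage I-III against stage IV), age stratum and baseline value. For yes/no outcomes, use the corresponding regression.

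**In Section 6**, add entry route to the recorded baseline characteristics. The record review before outreach already has to establish it.

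**In reporting**, give sessions completed (navigation arm only) and follow-up survey completion (both arms) by entry route. For a feasibility trial this is useful whatever the balance turns out to be.

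**Optional, only if randomization has not started:** add entry route as a second stratification factor. If this is done, keep the adjusted model, because an unadjusted t-test after stratifying is conservative.

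**Reconcile separately:** the stage I-III query terms with stage IV eligibility; 60 in total with 40 per arm; and the differing rank of the efficacy outcomes in Sections 2 and 6.

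**Cost:** a few sentences and one data field, and one or two degrees of freedom in the model. Re-stratifying would add sparse cells, notably young stage IV patients, and slightly less even arms. No extra patients or visits are needed.
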